13.1	Clinical Study Report and Publication Policy .....	24
Appendix A – Study Site and Investigator List.....		25
Appendix B – Administrative Structure of Investigation .....		26
References .....		28

**Study Title: GE Cardiovascular Ultrasound Device****Evaluation****Study Number: 217021760****DOCUMENT AND VERSION CONTROL**

This section records all changes made to the protocol for a specific study. In the table below, record every relevant change by indicating what changes have been made.

Version	Date	Author	Comments/Changes
1.0	23/Aug/2021	[REDACTED]	Lead Medical Writer – Initial version.
2.0	14/Apr/2022	[REDACTED]	Lead Research Program Integrator, Ultrasound During review of the IDE application for this study, FDA requested modifications to the eligibility criteria, which are detailed in Appendix C (Amendment of Protocol Version 1.0 to 2.0)

**Study Title: GE Cardiovascular Ultrasound Device  
Evaluation**

**Study Number: 217021760**

---

**LIST OF ABBREVIATIONS AND TERMS**

AE	Adverse Event
ADE	Adverse Device Effect
AFAP	As Far As Possible
AMA	American Medical Association
CA	Competent Authority
CCG	Case Report Form Completion Guidelines
CFR	Code of Federal Regulations
CHF	Clinical History File (synonymous with e-Trial Master File)
CRF	Case Report Form
DCF	Data Clarification Form
DMP	Data Management Plan
EC	Ethics Committee
EDC	Electronic Data Capture
EU	European Union
FDA	United States Food and Drug Administration
GCP	Good Clinical Practice (see ISO 14155)
GDP	Good Documentation Practices
GE	General Electric
HCP	Health Care Provider
IB	Investigator Brochure
ICF	Informed Consent Form
IFU	Instructions for use
ISO	International Standards Organization
IQ	Image quality
LAR	Legally authorized representative
<hr/>	
PI	Principal Investigator
RPI	Research Program Integrator
SADE	Serious Adverse Device Effect
SAE	Serious Adverse Event
SPR	System Problem Report
UADE	Unanticipated Adverse Device Effect
US	United States
USADE	Unexpected Serious Adverse Device Effect

**Study Title: GE Cardiovascular Ultrasound Device****Evaluation****Study Number: 217021760****SYNOPSIS**

Sponsor:	General Electric Company, acting through its GE Healthcare (GE Healthcare) Business
Research Type:	This is an open label, prospective, non-randomized clinical research study at a single site.
Regulatory Status:	This is a pre-market – pilot stage research study of the following devices/products: Pre-market: Vivid E95 [REDACTED] ultrasound system; [REDACTED] transesophageal echocardiography (TEE) probe
Background and Rationale:	GE Healthcare (GEHC) manufactures the Vivid E95 – a general purpose ultrasound system, specialized for use in cardiac imaging. Feedback from real clinical use cases is required to optimize medical devices prior to device finalization and commercialization. The goal of this study is to collect user feedback and de-identified images from the investigational Vivid E95 [REDACTED] system and probes during transthoracic echocardiogram (TTE) and TEE exams. The results of this study are intended primarily for use in engineering evaluation and optimization of the device.
Procedures/Methods:	Eligible subjects will be enrolled into the study and positioned for their ultrasound exam. Standard clinical practice procedures will be followed using the standard of care device at the site to complete the clinically indicated exams.  After the clinically indicated exam, portions of the TTE and/or TEE exam will be repeated with the investigational Vivid E95 ultrasound device. Ultrasound scans in this study will take a similar amount of time and be performed in a similar manner as standard of care ultrasound exams at the site.  The device operator will store images from both ultrasound exams conducted with the standard of care device and the investigational device. Images collected with the investigational device will not be used for patient management.
Objectives:	The primary objective of this study is to collect user feedback and de-identified images from the Vivid E95 [REDACTED] ultrasound system and probes in TTE and TEE exams in a clinical setting. User feedback will include workflow, performance, user preference, image quality (IQ), device features, and open-ended feedback.  The safety objective of this study is to collect safety information, including type and number of AEs, SAEs, and device issues. No clinical efficacy endpoints will be assessed.

# Study Title: GE Cardiovascular Ultrasound Device Evaluation

Study Number: 217021760

Eligibility Criteria:	Inclusion criteria:	Exclusion criteria:
	

1) Has a clinical indication for a TEE and/or TTE procedure with an ultrasound device;

2) Has a weight of at least 5kg;

3) Is able and willing to comply with study procedures;

4) If less than 7 years old, has two parents or legally authorized representatives able and willing to provide written consent to participate.

5) If 7-17 years old, is able and willing to provide written assent to participate AND has two parents or legally authorized representatives able and willing to provide written consent to participate.

6) If 18 years old or older, is able and willing to provide written consent to participate.

	

1) Pregnant or suspected to be pregnant based on the opinion of a clinician investigator;

2) Expected to be at increased risk due to study participation (e.g. due to sensitivities, relative or absolute contraindication to TEE), in the opinion of a clinician investigator;

3) Previously participated in this study or are enrolled in another research study that could be expected to interfere with participation in study procedures;

4) History of esophageal surgery or known vascular ring; OR

5) Experiences any complications or difficulty with the initial TEE procedure performed using the standard device.

Sample Size and Sites:	Up to 100 subjects from one site will be included. This number is based on prior engineering development and testing experience of the Sponsor. This study will enroll the minimum number of subjects necessary to complete Sponsor engineering requirements for this stage of development and optimization of the device, which may be less than the maximum enrollment set forth in this protocol.	
Expected Subject Participation Duration:	The duration of subject participation is the time it takes to complete the ultrasound exam(s) (less than one day).	
Study Duration:	The study is expected to last approximately 6 months. Estimated start date (first subject in): January 2022 Estimated end date (last subject out): June 2022	
Study Completion:	The study will be considered complete when subject enrollment requirements are met per the Sponsor's determination.	

## **1. BACKGROUND AND JUSTIFICATION**

[REDACTED]

[REDACTED]

[REDACTED]

The goal of this study is to collect user feedback and de-identified images from investigational Vivid E95 [REDACTED] system and probes during TTE and TEE exams. The results of this study are intended primarily for use in engineering evaluation and optimization of the device and may be used for augmenting design verification and design validation.

GE Healthcare.

[REDACTED] Funding for this study will be provided by

# Study Title: GE Cardiovascular Ultrasound Device

## Evaluation

Study Number: 217021760

## 2. DEVICE DESCRIPTION

### 2.1 Identity, Mechanism, and Function

**Name:** Vivid E95 [REDACTED], [REDACTED] TEE probe

**Modality/Type:** Cardiovascular Ultrasound

**Manufacturer:** GE Healthcare

**Software version:** The most current version available will be used.

**Regulatory Status:** Pre-market – pilot stage

**Note:** A record of number of devices issued, along with applicable identification numbers (e.g., serial/lot/batch) and components/accessories used in this study will be retained by the Sponsor as part of the clinical history file (CHF), as required by applicable laws and regulations.

[REDACTED]

[REDACTED]

The research device, instructions for use, or packaging shall indicate that the research device is for use in a research investigation, per FDA 21 CFR §812.5 and other applicable laws and regulations.

The investigational device will be exclusively used for research purposes. Routine accessories necessary to perform ultrasound, such as ultrasound gels, may be provided by the site and used according to the site standard of care during this study. Additionally, software may be used for post processing of images.

### 2.2 Intended Use

The Vivid E95 ultrasound system is intended to be used for a variety of diagnostic cardiovascular procedures on pediatric and adult patients. Vivid E95 is a general purpose ultrasound system, specialized for use in cardiac imaging. It is intended for use by, or under the direction of a qualified physician for ultrasound imaging, measurement, display and analysis of the human body and fluid.

[REDACTED]

The procedures conducted in this study are intended for device development purposes.

## **2.3 Concomitant / Ancillary Administrations**

### **2.3.1 Medications and Biologic Products**

No medications or biologic products will be administered as part of study procedures. As part of the standard of care at the site, subjects may receive anesthesia. Clinically necessary medications for the subjects' prescribed medical procedure shall be administered per the site standard care and participation in this study will not alter their standard care.

### **2.3.2 Laboratory Tests and Sample Processing**

No laboratory tests or sample processing is planned as part of the study procedures.

## **2.4 Accountability**

Accurate and adequate records will be maintained for all devices, from time of shipment to the site until return or disposal of all devices issued by the Sponsor as part of this study, as required by applicable laws and regulations. The Principal Investigator will be responsible for the security and integrity of research devices at the investigational site during the study.

### **2.4.1 Issuance**

The research device will be provided by the Sponsor. No calibration/maintenance procedures are planned for this study. Software updates may be made during the study.

### **2.4.2 Disposition**

The device will be dispositioned after the study and returned to the Sponsor, per applicable laws and regulations.

## **2.5 Anticipated Risks and Benefits**

The device under study has undergone risk assessment, per International Standards Organization (ISO) 14971, and risks have been mitigated to levels as far as possible (AFAP). Verification of the system will be completed, including mitigation of hazards and functional changes impacting the study, and that the system device features operate as expected. Additionally, electromagnetic interference testing will have been completed to ensure the investigational device does not impact other electronic medical devices, and acoustic output verification testing will be completed to ensure that the energy output from the system is within acceptable ranges. The measures ensure that the devices used in the study are equivalent to systems that already meet the requirements for CE mark and are used for diagnosis outside of the USA. Validation of user requirements and expectations will be completed for the device.

The risks associated with the investigational device are not expected to be greater than those of similar procedures routinely conducted in clinical practice. Subjects will undergo procedures with both the standard of care device and the investigational device, so there may be an incremental risk associated with the double procedure. Post-trial care or follow-up is not required by this study.

Subjects are not expected to benefit directly from study participation. The results may benefit future patients by helping to optimize the device, accessories, and software. This may provide better imaging for pediatric patients in the future.

### **2.5.1 Risk Category and Rationale**

The [REDACTED] TEE probe, as used in this study, is considered a significant risk device per 21 CFR §812.3(m) because it does present a potential for serious risk to the health, safety, or welfare of a subject.

### **3. OBJECTIVES**

#### **3.1 Purpose of the Study**

The purpose of the study is to collect user feedback on the Vivid E95 [REDACTED] ultrasound system and probes during clinical procedures on the device's intended population in order to optimize the device.

##### **3.1.1 Primary Objective**

The primary objective of this study is to collect user feedback and de-identified images from the Vivid E95 [REDACTED] ultrasound system and probes in TTE and TEE exams in a clinical setting. User feedback will include workflow, performance, user preference, IQ, device features, and open-ended feedback.

##### **3.1.2 Safety Objective**

The safety objective of this study is to collect safety information, including type and number of AEs, SAEs, and device issues. No clinical efficacy endpoints will be assessed.

### **4. STUDY DESIGN**

#### **4.1 Summary of Study Design**

This is a pre-market, open label, prospective, non-randomized clinical research study conducted at one site in the United States. The study will be considered complete when subject enrollment requirements are met per the Sponsor's determination. The duration of subject participation is the time it takes to complete the ultrasound exam(s) (less than one day).

This study is not intended to support a comparative claim or test any hypotheses, such as superiority or non-inferiority, so no control group is necessary. All reasonable attempts will be made to control and minimize bias during the study. The study will not impact the clinically indicated scan used for clinical care. Subjects will be consecutively enrolled in this study as they present at the site for standard of care procedures. This type of sampling reduces, but does not eliminate, some risks of sampling bias. Additionally, site and Sponsor responsibilities are clearly defined to reduce additional biases during the conduct of study procedures.

#### **4.2 Study Population**

Subjects will be enrolled who meet all of the inclusion criteria and none of the exclusion criteria and are prescribed a standard of care procedure using an ultrasound device for a TEE exam, including either diagnostic or perioperative TEE, and/or a Transthoracic Echocardiography (TTE) exam. This population is representative of the general population that is expected for the device in clinical practice.

#### **4.3 Number of Subjects**

Up to 100 subjects may be enrolled in this study. This study will enroll the minimum number of subjects necessary to complete Sponsor engineering requirements for this stage of development and optimization of the device, which may be less than the maximum enrollment set forth in this protocol.

##### **4.3.1 Enrollment Schedule**

After the first 5 subjects are enrolled and complete study procedures, subject enrollment will pause. A progress update will be submitted to the EC, which will include safety-related information such as any adverse events, device deficiencies, or any other relevant issues that have occurred during the initial enrollment period. Subject enrollment will resume upon receipt of favorable opinion from EC.

## **4.4 Protection of Vulnerable Subjects**

Vulnerable subjects are individuals whose willingness to volunteer in a clinical investigation could be unduly influenced by the expectation, whether justified or not, of benefits associated with participation or of retaliatory response from senior members of a hierarchy in case of refusal to participate.

The Sponsor shall avoid improper influence on, or inducement of, the subject, monitor, any investigator(s), or other parties participating in, or contributing to, the clinical investigation.

All investigators shall avoid improper influence on, or inducement of, the subject, Sponsor, monitor, other investigator(s), or other parties participating in, or contributing to, the clinical investigation.

**Neonates, children, or minor subjects:** Neonates, children, and minor subjects under the age of 18 years old will be subjects in this study. These subjects are considered members of a vulnerable research population who are not legally competent to provide valid informed consent. This research will be approved by an EC, and two parents or legally authorized representatives (LARs), such as health care surrogate, attorney in fact, judicially appointed guardian, or proxy, must provide written informed consent for the child's participation. Assent will be obtained from minor subjects aged 7-17 years old.

The study activities cannot otherwise be performed without the use of vulnerable populations. Children have anatomical and physiological differences compared to adults, such as smaller and less developed anatomy, faster heart rate, and faster breathing rate, which affect ultrasound image acquisition. Children may also behave and move differently than adults during scans, which introduces additional challenges and variables. It is important to evaluate the device's performance in the intended population so it can be optimized for actual clinical use.

## **4.5 Eligibility Criteria**

### **4.5.1 Inclusion Criteria**

Subjects who meet all the following inclusion criteria may be enrolled:

- 1) Has a clinical indication for a TEE and/or TTE procedure with an ultrasound device;
- 2) Has a weight of at least 5kg;
- 3) Is able and willing to comply with study procedures;
- 4) If less than 7 years old, has two parents or legally authorized representatives able and willing to provide written consent to participate.
- 5) If 7-17 years old, is able and willing to provide written assent to participate AND has two parents or legally authorized representatives able and willing to provide written consent to participate;
- 6) If 18 years old or older, is able and willing to provide written consent to participate.

### **4.5.2 Exclusion Criteria**

Subjects who meet any of the following exclusion criteria will be excluded:

- 1) Pregnant or suspected to be pregnant based on the opinion of a clinician investigator;
- 2) Expected to be at increased risk due to study participation (e.g. due to sensitivities, relative or absolute contraindication to TEE), in the opinion of a clinician investigator;
- 3) Previously participated in this study or are enrolled in another research study that could be expected to interfere with participation in study procedures;
- 4) History of esophageal surgery or known vascular ring; OR

# **Study Title: GE Cardiovascular Ultrasound Device Evaluation**

**Study Number: 217021760**

---

5) Experiences any complications or difficulty with the initial TEE procedure performed using the standard device.

**Note:** It is not possible to assess exclusion criterion #5 prior to the point of enrollment; this exclusion criterion will be assessed during the initial standard care TEE procedure.

## **4.6 Recruiting and Screening**

Subjects will be recruited for potential enrollment in this study according to the standard procedures of the investigational site, unless otherwise specified by the Sponsor in this study protocol. All participation will be voluntary.

Subjects will be screened for enrollment in this study against the inclusion and exclusion criteria according to the standard procedures of the investigational site.

Following recruitment, a subject will be considered enrolled (the point of enrollment) once the subject or the subject's parents or LARs sign and date the informed consent form (ICF), including the informed assent form as applicable. Once enrolled, the subject will be assigned a unique subject number, which will not contain information that could identify the subject (such as subject name or date of birth). The unique subject number will be used to label case report form (CRF) data for the subject throughout his/her participation in the study.

## **4.7 Criteria for Withdrawal/Discontinuation**

A subject may withdraw from study participation at any time, for any reason. The Investigator may withdraw a subject at any time, for any reason. The reasons for withdrawal and discontinuation for any subject shall be recorded on a CRF. These will be reported to the Sponsor. The EC should be notified per their notification of subject withdrawal policy.

# **5. STUDY PROCEDURES**

## **5.1 Subject Preparation**

Study staff will confirm that the subject is eligible and complies with applicable site requirements prior to starting study procedures. No preparation beyond that required by the investigational site is required before procedures.

## **5.2 Description of Study Procedures**

Eligible subjects will be enrolled into the study and positioned for their ultrasound exam. Standard clinical practice procedures will be followed using the standard of care device at the site to complete the clinically indicated exams.

After the clinically indicated exam, portions of the TTE and/or TEE exam will be repeated with the investigational Vivid E95 ultrasound device. Ultrasound scans in this study will take a similar amount of time and be performed in a similar manner as standard of care ultrasound exams at the site. The additional investigational TTE and TEE scans will add no more than about 15 minutes to the procedure time. For subjects having TEE in conjunction with surgery or an interventional catheterization procedure, the additional investigational scans will occur simultaneously while the hospital staff are preparing for or performing the procedure to avoid any delay in care. Images collected with the investigational device will not be used for patient management.

The device operator will store images from both ultrasound exams conducted with the standard of care device and the investigational device.

After completion of the investigational ultrasound exam, the ultrasound system and associated probes will be cleaned and disinfected as applicable, according to site standard of care and specifications in Sponsor instructions provided to the site.

**Study Title: GE Cardiovascular Ultrasound Device Evaluation**  
**Study Number: 217021760**

---

The subject will be followed for adverse events (AEs) from the time the ultrasound exam begins with the investigational device to the time the subject leaves the scan room. Subjects may also contact the PI if they experience any additional symptoms after the study. Subjects will, if necessary, be provided with emergency care. In the event of any device issues, the event will be recorded.

Any AEs or device deficiencies/complaints observed by the operator will be reported to GEHC.

### **5.3 Follow-up**

Study enrollment will end after the subject has completed his/her investigational ultrasound exam. AEs reported to the site will be followed until resolution. No other follow-up procedures will be conducted.

Any data, including de-identified images, collected for the subject, up until the time of withdrawal or discontinuation, may still be provided to GEHC, unless the subject requests that their data not be used. The site shall document all requests by subjects regarding their data use.

## **6. STUDY DATA COLLECTION AND ASSESSMENTS**

Only data relevant to the conduct of the study shall be collected by the Sponsor.

### **6.1 Primary Assessment**

The device user will save the images (raw DICOM) during the conduct of the procedures. Device users performing the scans will periodically be asked to provide feedback on User Survey forms prepared by the Sponsor.

Minimal data will also be collected per subject on a CRF, including:

- Date of consent/assent;
- Confirmation of eligibility, including age and weight;
- Investigational exam information [device user, procedure(s) completed (TTE and/or TEE), start/stop times, and probes used].

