## **9.6 Suspension/Early Termination of the Study**

The Sponsor, PI, EC, or regulatory authority may suspend or terminate the study prematurely for various significant and documented reasons. Reasons for suspension or termination may include but are not limited to insufficient participant recruitment, updated risk profile impacting subject safety, alterations in accepted clinical practice impacting study procedures, updates to software or improvement of product technology, early evidence of benefit or harm of the research product, or serious or repeated deviations by the investigator.

The decision to suspend or terminate the study should be shared in writing with all parties described above.

If the reason for study suspension is resolved, the deciding party shall inform all appropriate parties of the decision and actions to resume study procedures.

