### **10.2 Sample Size Determination**

Sample size is based on the Sponsor's previous clinical experience and the number of user surveys required by engineering. This number is based on prior engineering development and testing experience of the Sponsor. Each ultrasound exam may utilize different combinations of features and probes, so multiple exams are necessary to assess all features. In addition, enrolling multiple subjects will allow the device to be evaluated across various characteristics (such as age, body habitus, and pathology), which is important to optimize the device for its intended use in a diverse patient population.

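### Does Section 6.1 need to tie each user survey to an exam and a software version?

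*Protocol*

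**What the plan says.** Section 3.1.1 states the aim: "The primary objective of this study is to collect user feedback and de-identified images from the Vivid E95", in transthoracic (TTE) and transesophageal (TEE) exams. Feedback and images are thus the two products of the study.

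Section 6.1 covers the feedback with: "Device users performing the scans will periodically be asked to provide feedback on User Survey forms prepared by the Sponsor". The same section lists the data to be taken for each subject on a CRF, among them "Investigational exam information [device user, procedure(s) completed (TTE and/or TEE), start/stop times, and probes used". That list is introduced as examples of what is included, not as a closed set.

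Section 4.6 gives the scope of the identifier: "The unique subject number will be used to label case report form (CRF) data for the subject". It does not mention the User Survey forms.

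On software, Section 2.1 says "The most current version available will be used" and Section 2.4.1 says "Software updates may be made during the study". Section 9.6 names "updates to software or improvement of product technology" among the possible reasons to suspend or terminate the study.

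Section 10.2 explains why more than one exam is wanted: "Each ultrasound exam may utilize different combinations of features and probes, so multiple exams are necessary to assess all features". It adds that several subjects let the device be evaluated across age, body habitus and pathology.

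**The concern.** The reason given in Section 10.2 for repeated exams is variety: different probes, features and patients. That variety is informative only if a rating can be placed against the exam it describes. If a user fills in one form after several mixed exams and gives one Likert score, the score cannot be split afterwards between a small child and an adult, or between one probe and another. If the software was updated in between, it cannot be split into before and after either.

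The protocol states no survey key that would prevent this. A statistical analysis plan would not supply one, because Section 10.3.1 places survey data outside any such plan, and no analysis can restore a link that was never recorded. Section 1 also allows the results to augment design verification and validation, where the software version behind a rating is ordinary context. At stake is the usefulness of the feedback half of the primary objective.

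**Working it through.** The protocol gives no figure to reproduce here. The numbers of surveys, users, software versions and surveys per exam are all unstated, so the check is a reading of the relevant sections against each other.

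1. **Is a link stated?** No. Section 6.1 gives only periodic timing. Section 4.6 applies the subject number to CRF data. The device record in Section 2.1 is kept at study level (serial, lot or batch numbers and components) and does not give a version for each exam.

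2. **Is a link ruled out?** No. Section 6.1 leaves the content of the form to the Sponsor, and the form is not shown. The CRF list is open-ended. Nothing prevents either document from carrying a date, user, probe or version.

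3. **Where would such a field normally be specified?** In the forms and the data management documents. Section 11.1 gives data management to the Sponsor. Section 11.1.1 has the Sponsor supply the CRFs, train staff on them and, if useful, issue completion guidelines. The abbreviation list includes a data management plan. Section 11.1.2 requires that data be controlled and traceable. None of these names a survey key, but they show who would set one. The exclusion in Section 10.3.1 concerns how survey data are analyzed, not what is printed on the form.

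4. **What can be recovered from what is listed?** The CRF records device user, procedure, start and stop times and probes for each investigational exam, under a subject number. Survey respondents are the users who performed those scans. A dated form with the user's name could be matched to that user's exams, and the Sponsor could match the date to its own software updates. This depends on forms being dated and identified, which the protocol does not say. It would not separate exams covered by a single rating.

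5. **Does any result depend on it?** Section 10.1 tests no hypothesis, Section 10.3 plans no statistical analysis, and Section 10.3.1 describes survey data as Likert scales and qualitative feedback. Safety reporting has its own route in Section 8. Images are stored at the exam from both devices (Section 5.2) and go to the Sponsor with associated data (Section 12.1.1), so the image half of the objective is untouched.

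6. **Would requiring one survey per exam be a clear gain?** Section 10.2 sets no survey unit, so periodic feedback contradicts nothing. Assume 1 to 2 minutes per form. With 100 subjects and one form each, user time is 100 × 1 = 100 to 100 × 2 = 200 minutes. A subject may have both TTE and TEE. If each counts as an exam, there are up to 100 × 2 = 200 forms, or 200 × 1 = 200 to 200 × 2 = 400 minutes. The burden is modest, but many short forms in place of fewer considered ones is a trade-off in formative work, not a correction.

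7. **Would a lighter rule help?** Listing on a periodic form all the subjects it covers would not make one combined rating attributable to any of them.

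**The case for a change.** The best argument for amending Section 6.1 is that feedback is a main product of the study, that linkage is cheap to record at the time and may be unrecoverable later, and that the traceability sentence in Section 11.1.2 names no key. Section 8.5 adds some weight: feedback given to meet the objective is not treated as a device deficiency, so it falls outside the investigation and documentation set out there, and the survey becomes its main stated record. Section 10.2 also rests the sample size partly on the number of surveys engineering needs, while the relation of surveys to exams is left open.

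The factual part of this stands: the protocol does not state the link, and software version is not a listed exam item. The step from there to lost information does not. It requires that the unseen form lacks these fields, that one form mixes exams or straddles an update, and that the form does not separate them. The documents establish none of the three. If the Sponsor wished, it could record software version with the exam information and put the date, device user, probe and version on each form, or confirm that the forms already carry them. That is form design within its existing responsibilities and needs no amendment.

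**Conclusion.** No change to the plan is called for. Section 6.1 is brief where it could have been fuller, but the missing detail is of a kind that a Sponsor preparing its own forms, for its own device and its own engineers, would sensibly fill.

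No estimate, test, safety count or conclusion is affected. The possible loss is in how finely Likert and free-text feedback can be sorted by probe, patient type or software version, and its size cannot be derived because the numbers of forms, users and updates are not given.

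The judgement rests on two assumptions: that the survey form or data management documents carry ordinary identifiers such as date and user, and that the Sponsor keeps track of its own software updates. If neither held, some feedback would be harder to interpret, but the study would still meet its stated aim of collecting feedback and images.
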